CONFIDENTIAL AND PROPRIETARY

Information provided herein is the property of the University-Hospital of Brescia. Nothing herein is to be reproduced, published, or disclosed to others in any way without the prior expressed written permission of the University-Hospital of Brescia.

Title of Study: Clinical and microbiological efficacy of *Lactobacillus reuteri* in the supportive therapy of periodontitis: a 6 months Randomized Controlled Trial study.

Type of Study: Clinical and microbiological

Protocol No: PROTOCOL #PERIOPRO

Expected study start date: APRIL, 2020 (study initiation)

Study Location/Country: Brescia, Italy

Study Originator(s)/ Contact (name, phone, fax): [name], [name], [contact], email: [contact]

Test Products w/ PDM Numbers:

CE marked Medical Device to be used as an adjunct therapy to standard in patients with moderate to severe periodontal disease (Confidential information).

Study Title:	Clinical and microbiological efficacy of Lactobacillus reuteri in the supportive therapy of periodontitis: a 6 months Randomized Controlled Trial study.
Study sites:	[name] (lead site) University-Hospital of Brescia Brescia, Italy.
Study Phase:	IV.
Name of Medical Device:	GUM® Periobalance® (SUNSTAR SUISSE S.A. [name])
Objective:	The objective of the clinical study is to assess the efficacy of the addition of Lactobacillus reuteri in the supportive therapy of periodontitis in terms of reduction of PD (Probing Depth).
Patient Population:	44 periodontal patients, systemically healthy, male and female adults (18 – 75 years), with history of periodontitis grade B or C and stage III or IV, with at least 2 residual sites/pockets with probing depth ≥ 6 mm or pockets of 5 mm with bleeding on probing in two different quadrants.
Structure:	Parallel arms: Number of treatments: 1 (after a session of non-surgical supportive therapy one group takes probiotic (Lactobacillus reuteri) lozenges 2 times a day for 21 days, another group takes placebo lozenges 2 times a day for 21 days).
	Duration of study: 36 months.
Number of Centers:	One.
Blinding:	Patient, Examiner, Operator and Statistician -Blind.
Method of Patient Selection:	Periodontal pockets: at least 2 sites with probing depth ≥ 6 mm or pockets of 5 mm with bleeding on probing in two different quadrants.
Total Sample Size:	44 adult subjects will be recruited (randomized) to participate in this study, with 40 expected to complete the study.
Primary Efficacy Variable:	Primary outcome measure will be the changing of PD in millimeters.

Clinical and microbiological efficacy of *Lactobacillus reuteri* in the supportive therapy of periodontitis: a 6 months Randomized Controlled Trial study.
PROTOCOL #PERIOPRO

Protocol Date: JAN 13, 2020

Protocol Approval

Signature Page

[name]
University-Hospital of Brescia, Italy

Date

ADDRESSES AND RESPONSIBILITIES

Addresses

Study Centres:	Section of Periodontics, School of Dentistry, Department of Surgical Specialities, Radiological Science and Public Health University of Brescia [name]
	[name] (Principal Investigator) [contact] Email: [contact]
Study coordinator:	[name] Section of Periodontics, School of Dentistry, Department of Surgical Specialities, Radiological Science and Public Health University-Hospital of Brescia Brescia, IT
Data Management & Monitoring:	[name] Section of Periodontics, School of Dentistry, Department of Surgical Specialities, Radiological Science and Public Health University-Hospital of Brescia Brescia, IT
Statistician:	[name] Unit of Biostatistics and Bioinformatics, Department of Molecular and Translational Medicine University of Brescia Brescia, IT
Microbiologist:	[name] Head of the Department of Preventive Dentistry Professor in Oral Microbial Ecology Academic Centre for Dentistry Amsterdam Vrije Universiteit Amsterdam and University of Amsterdam Amsterdam, the Netherlands

Responsibilities

The **principal investigator's** responsibilities are described in detail in ISO norm 14155:2011 for the clinical investigation of medical devices for human subjects.

The role of the principal investigator is to implement and manage the day-to-day conduct of the clinical investigation as well as ensure data integrity and the rights, safety and well-being of the subjects involved in the clinical investigation.

The principal investigator shall be qualified by education, training and experience to assume responsibilities for the proper conduct of the clinical investigation. In particular, the principal investigator is responsible for:

- qualification of investigation site;
- communication with Ethics Committee;
- compliance with Informed Consent process;
- compliance with Clinical Investigation Plan.

Under the direct supervision of the Principal Investigator, certain duties may be delegated during the course of the study. These responsibilities will be documented on the transfer of responsibilities form maintained in the Investigator Site file.

The **Statistician** will be responsible for:

- sample size calculation;
- statistical plan;
- statistical section of the protocol;
- statistical evaluation;
- final statistical report.

The **Microbiologist** will be responsible for:

- sample microbiological processing and analysis;
- final microbiological report.

OBJECTIVE

The study will be performed to assess the efficacy of the addition of *Lactobacillus reuteri* containing lozenges in the supportive therapy of periodontitis in terms of reduction of PD (Probing Depth).

INTRODUCTION

Probiotics are defined as 'live microorganisms which, when administered in adequate amounts, confer a health benefit on the host'. The influence of probiotics on pathogens flora can derive from three principal modes of action: innate and acquired host defense modulation, production of antibacterial substances and competitive exclusion mechanism. In particular, *Lactobacillus reuteri* has been studied for its antibacterial and anti-inflammatory properties.

It is a heterofermentative bacterium and the distinct strains have different characteristics. In particular it acts as an antibiotic, induces oxidative stress on pathogens, is resistant to proteolytic and lipolytic and present anti-inflammatory properties.

Literature pointed out to potential effectiveness of *L. reuteri* as an adjunct to non-surgical periodontal therapy in initial treatment of periodontitis patients but underlined the limits of their conclusions due to the heterogeneity of the studies and to the few patients included. There is thus a need for more long-term randomized controlled studies. In particular, only one study addressed the use of this probiotic during the supportive therapy and in particular in patients with severe forms of periodontitis but few patients were included.

Patients meeting the criteria of periodontitis stage III and IV, grade C are considered to be affected by severe and advanced forms of periodontitis with a rapid rate of progression. This group of patients could particularly benefit from supplements in the maintenance of periodontal health.

STUDY OUTCOMES

- a. Primary outcome measure: change in PD
- b. Secondary outcomes:
 - changes in the following clinical parameters: Pocket closure, REC (Clinical Gingival Recession), CAL (Clinical Attachment Level), BOP (Bleeding on Probing), PI (Plaque Index).
 - Risk progression of the periodontitis and the need of periodontal surgery.
- c. Microbiological outcomes: changes in microbial composition and proportion of sequences identified as *Lactobacillus reuteri* in the deepest residual pockets.

STUDY POPULATION

Forty-four (44) adults, aged 18-75 years, will be entered into study (randomized). It is expected that forty (40) subjects will complete the study.

Randomized subjects who deviate from the protocol (major protocol deviation) and, for this reason, are excluded from the analysis, will be replaced to guarantee that the sample required for the analysis (40) is reached.

Patients will be treated at the Department of Surgical Specialities Radiological Science and Public Health, School of Dentistry, Section of Periodontics, Brescia, Italy from 04/2020.

Inclusion Characteristics

- Signed Informed Consent Form.
- Male and female subjects, aged 18-75 years, inclusive.
- Good general health (free of systemic diseases such as diabetes, HIV infection or genetic disorder, ongoing malignant disease of any type that could influence the outcome of the treatment and might interfere with the evaluation of the study objectives).
- History of periodontitis staging III or IV grading B or C
- At least 2 sites with probing depth ≥ 6 mm or pockets of 5 mm with bleeding on probing in two different quadrants.
- Previous periodontal non-surgical treatment at least 3 months maximum 6 months.
- Availability for the 6-month duration of the study for an assigned subject.

Exclusion Characteristics

- Not willing to follow the agreed protocol.
- Presence of orthodontic appliances.
- Smokers more than 10 cigarettes per day
- Chronic obstructive pulmonary disease and asthma.
- Tumors or significant pathology of the soft or hard tissues of the oral cavity.
- Current radiotherapy or chemotherapy.
- Pregnant or lactating women.
- Current or past (within 3 months prior to enrollment) assumption of medications that may influence periodontal conditions and/or interfere with healing following periodontal treatment (i.e., corticosteroids, calcium channel blockers, systemic antibiotics, ...).
- History of allergy to Erythritol or chlorexidine.
- Restorations on the teeth to be treated which may interfere with treatment administration and/or scoring procedures, at the discretion of the examiner.
- Use of systemically administered antibacterial agents or probiotics 3 months prior to enrollment.

A written informed consent will be obtained from each included patient after explanation of the risks and benefits of participating to this study. No change in the trial design will be made after approval of the Ethical Committee.

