1. STUDY DESIGN

The study design was chosen according to the current standards required by ISO, GCP and according to national requirements.

- a. A Parallel-Arm, Statistician, Operator and Examiner are blinded, RCT will be established;
- b. The RCT will be run as mono-center;
- c. A total of 44 subjects will be recruited to participate in the study. It is expected that all of 40 subjects will complete the study in total;
- d. Admission into the study will be via rolling admission (estimated recruitment time: 12 months);
- e. Each subject must have at least 2 residual sites/pockets with probing depth ≥ 6 mm or pockets of 5 mm with bleeding on probing in two different quadrants;
- f. Each subject will follow the following treatment protocol:
 - i. – Visit 1 (Screening): (within 29 days prior to baseline) – consent secured; screening and entry into study; baseline data collection; full periodontal charting (full-mouth PD, REC, BOP, PI); identification the sites for microbiological sample.
 - ii. – Visit 2 (T0 – Baseline Visit+Treatment): collection of microbiological samples from the two deepest sites in two different quadrants. All patients receive a full mouth periodontal treatment (GBT) and OHI (oral hygiene instruction). According to the list of randomization the patient will be allocated into one of the two arm of probiotic treatment: study lozenges are given to all patients to consume at home. The patients are instructed to dissolve these on their tongue twice a day, preferably after brushing, for 3 weeks. The patients of the probiotic group will receive probiotic lozenges containing *Lactobacillus reuteri* DSM 17938 and *Lactobacillus reuteri* ATCC PTA 5289 (a minimum of 2×10^8 colony-forming units L. reuteri Prodentis/lozenge, BioGaia AB). The patients of the control group will receive control lozenges without live bacteria. Furthermore, the probiotic and control lozenges will be identical in taste, texture and appearance.
 - iii. – Visit 3 (T1) – 3 weeks: the participants will be asked to return the empty packages of the study medication to examine the adherence. At that time, side effects will also be questioned by the examiner by means of an open question. Collection of the

microbiological sample will be performed from the same subgingival sites as during Baseline (T0) and reinforcement of OHI.

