zOTUs that taxonomically will be assigned to genus *Lactobacillus*, will be analyzed separately, in order to assess if the probiotic strains have established in the oral cavity. For this, first, a phylogenetic tree will be created based on the representative sequence of each zOTU. Sequences that will be phylogenetically related to *L. reuteri* 16S rRNA gene fragment amplified, will be marked as potential probiotic sequences. Relative abundances of all genus lactobacillus sequences and *L. reuteri* sequences between groups per timepoint will be compared.

Concomitant Therapy

A necessary concomitant medication or therapy is permitted as long as it is not excluded in the exclusion criteria. Every medication has to be reported in the CRF (Appendix 1) and in the

Concomitant Medication form (Appendix 2). All changes during the study are to be reported in the CRF. Usage of prohibited therapy will lead to the exclusion of the subject.

Blinding and Randomization

Blinding: The statistician will be blinded to the group identification. The patient and the operator will not know the treatment. Knowledge of the randomization list will be limited to the persons responsible for creation of the randomization list, provider of randomization numbers to study site, and delivery of the test/control treatment until the last subject (i.e. final examination of the last subject), quality control and verification of the CRFs is completed.

Randomization and allocation concealment: The randomization of the study protocols will be performed by a staff member who is not further involved in this study. This will be done based on a computer-generated table (www.randomization.com) that links each patient to one of the treatment groups. The same staff member will be responsible for blinding the study products. This will be done by labelling the packaging of these products with a letter indicating the treatment group. Additionally, the jars containing the lozenges will be identical in appearance and non-transparent. When a patient will be included in the study, the study medication will be handed out to the researcher according to group to which that patient will be assigned based on the patient number and the randomization list. The similarity of the packaging, and the identical appearance, texture and taste of the study products make the double-blinding of the researcher and patient possible.

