4. STATISTICAL ANALYSIS

Sample size determination

The sample size was calculated via simulation assuming an expected difference of 1mm pocket probing depth and using a linear mixed effect model considering patients as random effects. We simulated 1000 realizations of pocket probing depth applying the data correlation structure from the AgPro study (fixed effect correlation = -0.664; random effects intercept SD = 0.974; random effects residual SD = 1.65) and assuming an average of 7 experimental sites per patient. A sample size of 20 patients per group allowed for a power of at least 80% at the chosen $\alpha = 0.05$. Taking into account a dropout rate of 10%, we estimated a total sample size of 44 patients. The simulation was performed using R (version 3.6.1).

Statistical Analysis

Data will be described using standard summary statistics such as mean and standard deviations for quantitative variables and proportions for categorical variables. The primary outcome is pocket probing depth (PPD). Only the sites with PPD greater or equal to 6mm at baseline were considered or PPD equal to 5mm and BoP+. For the primary outcome a linear mixed effect model will be used considering patients as random effects.

Secondary continuous outcomes will be modelled using a linear mixed model while generalized mixed models will be applied to categorical outcomes. Data will be modelled both using a 1-level hierarchical model (clustering level: patient) after averaging the outcome variables within subject, and using a 3-level (patient, tooth and site) hierarchical model. Results will be expressed as estimates and relative 95% confidence intervals. A significant level of 5% will be used for all the comparisons and all analysis will be performed using R (version 3.6.1 or higher).

Evaluation of Safety

The following safety variables will be used for the evaluation of safety:

- Adverse events (AE);
- Adverse reactions (AR).

The total number of AEs and the total number of AEs at least possibly related to the study treatment, as well as the total number of patients affected by at least one adverse event will be calculated per treatment group.

The type of AE classified by organ system (according to MedDRA terminology) will be tabulated. Serious and/or unanticipated adverse events and AEs resulting in discontinuation or reduction/withdrawal of the study treatment will be presented separately.

Safety analysis set

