Safety summaries will be based on the safety analysis set which will consist of all patients who received the test/control treatment.

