7. DOCUMENTATION AND DATA MANAGEMENT

Data collection in the case report form (CRF)

All study data will be recorded in the case report forms identified by the subject number. Only the principal investigator, co-investigators, or designated study personnel may make entries in the case report forms.

The Investigator has to identify all data that were directly recorded into the CRF and to be considered to be source data.

The CRFs will be checked for completeness and plausibility by the PI. The Investigator will resolve any queries.

Investigator Site File (ISF)

The ISF includes all documents that are required for the clinical study. During monitoring, the ISF will be checked regularly for completeness and actuality. After the clinical trial is finished or stopped, the ISF has to be stored 15 years in the study center.

Data Management

Data extraction from CRFs into a single, electronic database is performed by examiners. Discrepancies are to be clarified and corrected by authorized persons by means of documented data queries between Statistician and Investigator(s).

After the study is finished and before data are analyzed, a blind data review meeting will be held between the investigator and the statistician. When the database has been declared to be complete and accurate, it will be locked. Any changes to the database after this procedure can only be made by joint written agreement among the clinical trial leader, the trial statistician, and the co-investigators.

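### Randomised patients with an undefined major protocol deviation are to be excluded from the analysis and replaced, and no efficacy population is named, so the primary comparison is not of the groups as randomised

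*Combined protocol and SAP*

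**What the plan says.** The rule stands in the Study Population section: "Randomized subjects who deviate from the protocol (major protocol deviation) and, for this reason, are excluded from the analysis, will be replaced", and the sentence ends with its purpose, "to guarantee that the sample required for the analysis (40) is reached". The same section has 44 patients randomised and 40 expected to complete.

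Section 4 (Statistical Analysis) specifies the primary model: "For the primary outcome a linear mixed effect model will be used considering patients as random effects". It states which sites are eligible, but not which patients, and gives no rule for missing outcomes. The only analysis set it defines is for safety: "Safety summaries will be based on the safety analysis set which will consist of all patients who received the test/control treatment".

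Two other passages bear on what a deviation might be. Section 2 (Concomitant Therapy) says: "Usage of prohibited therapy will lead to the exclusion of the subject". Section 6 allows withdrawal of a patient who does not substantially comply with the protocol. Neither mentions exclusion from the analysis.

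There are safeguards. Section 1 says that "the probiotic and control lozenges will be identical in taste, texture and appearance". Section 2 (Blinding and Randomization) says: "Knowledge of the randomization list will be limited to the persons responsible for creation of the randomization list", together with those who provide the numbers and deliver the treatment. Section 7 says that before analysis "a blind data review meeting will be held between the investigator and the statistician".

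**The concern.** Randomisation protects the comparison only while patients are analysed in the groups that it formed. Protocol deviations arise after randomisation. Adherence and side effects, for example, are assessed at three weeks, when the lozenge course ends. If the treatment affects who deviates, and deviators differ in outcome, removing them leaves two groups that are no longer comparable. A replacement is a different patient and does not undo the selection.

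At stake are the primary p-value and confidence interval. With about 22 patients per arm, each exclusion removes 1/22 = 4.5% of an arm. Because the criterion is not defined, a reader of the results could not check which patients the rule removed, or whether it was applied alike in both arms. The direction of any bias cannot be known in advance.

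**Working it through.** **Inputs from Section 4.** Between-patient SD 0.974 mm, residual SD 1.65 mm, 7 sites per patient, difference 1 mm, 20 patients per group, power at least 80%, alpha 0.05 (taken as two-sided), dropout 10%.

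**The plan's own figure.**
- SD of a patient mean = sqrt(0.974² + 1.65²/7) = 1.157 mm.
- SE of the difference at 20 per arm = 1.157 × sqrt(2/20) = 0.366 mm.
- Power at 1 mm is 78.1% by the normal approximation and 75.9% by noncentral t. A simulated maximum-likelihood Wald test gives 79.2%. The Monte Carlo standard error of 1,000 runs is about 1.3 points.
- 40 × 1.10 = 44.

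The stated sample size is thus reproduced approximately. The concern does not rest on an arithmetic error.

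**Size of a possible bias.** The protocol gives no deviation rate, so these are scenarios. Assume no true effect and a correlation rho of 0.3-0.5 between the tendency to deviate and the outcome. If a proportion p of an arm is excluded, the mean of those retained moves by

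rho × 1.157 × φ(z)/(1 − p), with z the upper p point of the standard normal.

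The factor φ(z)/(1 − p) is 0.109 at 5%, 0.195 at 10%, 0.274 at 15% and 0.300 at 16.7%. The bias is the difference between arms. For 15% versus 5% at rho 0.5 it is 0.5 × 1.157 × (0.274 − 0.109) = 0.096 mm.

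A simulation of 100,000 trials per case (44 randomised 22/22, later replacements assigned 1:1 at random, t-test on patient means, Monte Carlo error about ±0.14 points) was checked against noncentral t with 38 df:

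| Deviation rates by arm | Shift, rho 0.3 / 0.5 (simulated) | Type I error, simulated | Type I error, noncentral t |
|---|---|---|---|
| 10% vs 10% | – / 0.00 mm | – / 4.9% | 5.0 / 5.0% |
| 10% vs 5% | 0.029 / 0.051 mm | 5.08 / 5.29% | 5.1 / 5.2% |
| 15% vs 5% | 0.058 / 0.096 mm | 5.36 / 5.82% | 5.3 / 5.7% |
| 16.7% vs 0 | 0.101 / 0.173 mm | 5.88 / 7.41% | 5.9 / 7.5% |

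With rates of 10% versus 5% but no correlation with outcome, the shift is 0.00 mm and the type I error 5.1%.

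The simulation analysed the first 40 analysable patients. That cut is an assumption: the protocol says that 40 is to be reached, not that further patients are dropped. Without it, about 40.6-41.9 patients are analysed on average and the type I error hardly changes. Replacement was triggered in only about 6-46% of simulated trials, so the figures mostly measure exclusion.

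**Power if everyone is analysed as randomised** (noncentral t / normal). The smaller effects are assumed dilutions; the protocol gives no dilution rate.

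| True difference | All 44 give outcome data (22 per arm) | 20 per arm give outcome data |
|---|---|---|
| 1.0 mm | 80.0 / 81.8% | 75.9 / 78.1% |
| 0.95 mm | 75.9 / 77.8% | 71.6 / 73.8% |
| 0.9 mm | 71.3 / 73.3% | 66.9 / 69.2% |

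The right-hand column is what the planned 10% dropout implies. Dropouts who have three-month data would recover part of the gap.

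**The case against.** The strongest reply has four parts.

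First, the sentence is a replacement rule. It covers deviators who are excluded and does not say that every major deviator must be. That is a fair reading of the grammar. Even so, it presupposes exclusion from the analysis, and nothing in the protocol states an as-randomised analysis that would override it.

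Second, the Responsibilities section lists a statistical plan separately from the statistical section of the protocol, and efficacy sets may be defined there. This cannot be excluded. If that plan analyses patients as randomised, the Study Population sentence contradicts it and still needs editing.

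Third, lozenges are identical, the patient, operator, examiner and statistician are blinded, and treatment lasts three weeks. This makes knowing, arm-dependent classification unlikely and stands as a reason to expect little bias. It does not stop the treatment itself from affecting adherence, tolerability or use of other medication. Section 7 also does not say that the blind review classifies deviations.

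Fourth, the inflation is small in most scenarios. This stands too, and it limits how strongly the point can be put.

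A reader might also infer that Sections 2 and 6 remove patients from the analysis. They do not say so. They are only the nearest, partial guides to what a deviation is.

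**Conclusion.** The point holds as a defect of specification. An explicit rule takes randomised patients out of the analysis on an undefined criterion, and no named efficacy population corrects it. Confidence is high for the rule and the gap, and low for the size of any bias.

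A reader might infer that the primary result will be biased, or that the false-positive rate will be seriously inflated. The documents do not support that. They give no deviation rate and no sign that deviations will differ by arm. Under the assumptions above, moderate imbalance leaves the type I error between about 5.1% and 5.8%. It reaches 7.5% only when about one patient in six is excluded from one arm and none from the other, at the higher correlation. A reader might likewise infer a particular split of the 40 between arms. The sentence fixes only the total, and no range of arm sizes follows from it.

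This should be fixed, but it is not fatal to the trial.

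**What to change.** - **Section 4:** state that the primary efficacy analysis includes all randomised patients in the arm assigned, using all available probing data from three and six months (T2 and T3) in the mixed model, and state the missing-at-random assumption.
- **Study Population:** delete the exclusion-and-replacement sentence.
- **Deviations:** define a major protocol deviation before unblinding, for example at the Section 7 blind data review, and report the deviation-free set as a sensitivity analysis only.
- **Sections 2 and 6:** reconcile with this for data retention only, so that scheduled charting data are kept unless consent is withdrawn. The clinical withdrawal rules stay with the sponsor.

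The cost is wording, charting of deviating patients at visits already scheduled, and some dilution of the effect if deviators benefit less. The power tabulated above should be quoted with its condition: 80.0/81.8% at 1.0 mm needs outcome data from all 44 patients, and it is 75.9/78.1% if 20 per arm provide them. No increase in sample size is proposed.
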